Accumulating evidence has also identified a link between HCV infection and the development of diabetes. The mechanism of this link appears to be an independent association between HCV infection and insulin resistance (Aytug S, et al, *Hepatology*. 2003; 38:1384-92; Delgado A, et al, *Transplantation* in press 2004). Recent work by us (Delgado A, et al) has demonstrated that insulin resistance in post-liver transplant recipients is correlated linearly with HCV viral load. A recent study from a transgenic mouse model has also demonstrated that HCV core protein expression can lead to insulin resistance in the absence of significant liver pathology, implying that viral infection itself can produce insulin resistance in addition to any effects produced by accompanying inflammation and fibrosis (Shintani et al, *Gastro* 2004; 126:840). Because the HALT-C trial represents a relatively uniform group with respect to histology, and all patients were treated with the same lead-in antiviral therapy, this group represents a unique cohort to test the hypothesis that virologic clearance is associated with improvements in insulin resistance.

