- c) Quantitative alcohol consumption during the study will be assessed every 6 months, Form #42, Alcohol Use Questionnaire.
- d) ♦ New diagnosis of diabetes, and/or hyperlipidemia during the study, Form #30, Local Lab, and Form #10, Study Visit.
- e) ♦ Concomitant medications that may induce hepatic steatosis, Form #12, Medications Interview.

Serial laboratory tests will be performed per protocol:

- a) Liver panel at each visit, Form #30, Local Lab.
- b) HCV RNA every 3 months, Form #31, Central Lab – HCV RNA.
- c) Fasting blood glucose every 6 months, Form #30, Local Lab.
- d) Fasting triglyceride level every 6 moths, Form #30, Local Lab.
- e) ♦ Fasting insulin level at the end of year 2 (M24) Excel file, with Fasting Insulin results.

Liver biopsies obtained at the end of year 2 (M24) and year 4 (M48) will be assessed for hepatic inflammation, fibrosis, iron and steatosis.

To address aim 6, all non-diabetic patients with TW 20 response followed until TW 60 will be included. A group of matched (BMI, race, HCV genotype) non-diabetic controls with no virologic response at TW20 will also be studied if a difference in IR is detected at TW 60 between patients with SVR and relapsers.

1. Serial clinical data at baseline, TW20, TW 48, and TW 60 for patients with TW20 virologic response, and data at baseline and TW20 for matched controls.
2. Serial laboratory tests: liver panel, HCV RNA, glucose, triglycerides as per protocol. Fasting insulin levels at TW00 and TW 60 for patients with TW20 response.

If results show a difference in IR at TW60 between patients with SVR and relapsers, fasting insulin levels at TW20 will also be tested in study subjects and matched controls.

Specimen Collection, Handling, and Shipping:

- **Blood collection and processing for insulin assays at baseline and at year 2 (M24)**

1. Collect blood in a red top tube – 7mls (Do NOT use tubes that have EDTA coating).
2. Allow the blood to clot for at least 30 minutes – this does not necessarily have to be on ice if not available (blood can be allowed to clot for up to 2-2.5 hours).
3. Spin the tube for 10-15 minutes at 3000 RPMs.

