 - Alcohol consumption: life time alcohol consumption and consumption within the year prior to the liver biopsy.
 - Viral factors: HCV genotype, HCV RNA level.
 - Hepatic inflammation: ALT level and hepatic inflammation grade.
 - Iron: serum iron, TIBC and hepatic iron score.

Risk factor data such as BMI, life time alcohol consumption, diabetes status etc. will be coded as categorical or continuous variables as appropriate. These will be evaluated against the degree of steatosis (5 levels) and dichotomous collapsed steatosis codes (such as <33% vs \geq 33%) using the Cochran-Mantel-Haenszel chi-square test with one degree of freedom. Multivariate analysis will be performed using logistic regression analysis. These risk factor variables and the steatosis levels will similarly be evaluated against the fibrosis scores (6 levels). Because fibrosis will also be quantified morphometrically, it will also be analyzed as a dependent variable by analysis of variance.

4. These risk factors and their relationship to week 20 and sustained virologic response will also be assessed.

Univariate analysis will be carried out using categorical or continuous variables as appropriate. These will be categorized against dichotomous (W20 responder v nonresponder, SVR v no SVR (all W20 nonresponders will be categorized as no SVR)) variables using the Cochran-Mantel-Haenszel chi-square test with one degree of freedom. Multivariate analysis will be performed on significant variables identified in univariate analysis by logistic regression.

Longitudinal study

The following analyses will be performed:

1. Prevalence of hepatic steatosis in year 4 biopsies will be compared to the year 2 and baseline biopsies of all patients and separately for the treated patients and controls.
2. Changes in hepatic steatosis between year 4 and baseline biopsies will be compared for the entire cohort of patients, and separately for the treated patients and controls.
3. Correlation between changes in hepatic steatosis with changes in hepatic fibrosis.
4. Correlation between changes in hepatic steatosis and changes in other risk factors for hepatic steatosis such as BMI, alcohol consumption, triglyceride level, hepatic inflammation, and hepatic iron content.
5. Correlation between changes in insulin resistance (measured using the homeostasis model assessment (HOMA)) from baseline to week 60 of the lead-in patients and virologic response or relapse.

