We will compare HOMA-IR (calculated from fasting insulin and glucose levels) from subjects at entry into the lead in phase of HALT-C and compare week 60 samples from among responders (HCV RNA undetectable) and relapsers (HCV RNA +). Because of inherent insulin resistance among diabetic patients, we will confine the analysis to nondiabetic subjects (about 80%) of those with W60 samples. This would comprise about 250 subjects with available W60 sera. These would be evenly divided between responders and relapsers (125 in each group). Changes in HOMA-IR would be calculated between the responder and relapser groups. An advantage of studying W60 sera is that any confounding effects of PEGIFN and RBV on IR will be minimized, including weight loss on therapy. If differences can be discerned between the 2 groups, then it will also be of interest to perform W20 determinations among responders and nonresponders in a larger number of subjects. A secondary analysis would include assessment of the correlation between HOMA-IR and HCV RNA levels at baseline for all subjects and at W60 for relapsers, as well as correlation of virologic response or relapse with fasting glucose levels and HgbA1c in those persons with diabetes or impaired glucose tolerance (about 20% of the group).

PITFALLS AND LIMITATIONS

This study does not involve any additional invasive tests or time commitment from the trial participants. Most of the data required will be collected as part of the main trial, so we do not anticipate there will be any problem in conducting this study. It is possible that steatosis may have no role in the development of fibrosis/cirrhosis in patients with chronic hepatitis C. However, results from studies in patients with NASH and the recent report of Hourigan support that steatosis may be important in hepatic fibrogenesis. Patients in this study will all have significant fibrosis (Ishak score ≥ 3) and non-response to prior interferon therapy. Results of our study may not necessarily apply to other patients with chronic hepatitis C. However, the patients we will be studying are at greatest risks of developing fibrosis and cirrhosis, and any factor that can promote fibrosis should be easily demonstrated in this study.

REFERENCES

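### The Aim 6 comparison of insulin resistance between SVR patients and relapsers is described without adjustment for baseline BMI, race or HCV genotype, the factors on which the plan matches its conditional follow-on controls

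*Combined protocol and SAP*

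**What the plan says.** All references are to the combined protocol and SAP.

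- **Hypothesis (Background and Significance).** The cohort is to be used to "test the hypothesis that virologic clearance is associated with improvements in insulin resistance".
- **Analysis (Data Analyses, Longitudinal study, item 5 and the paragraph after it).** Item 5 is listed as "Correlation between changes in insulin resistance (measured using the homeostasis model assessment (HOMA)) from baseline to week 60", set against virologic response or relapse. The text then says the investigators will "compare week 60 samples from among responders (HCV RNA undetectable) and relapsers (HCV RNA" positive), and that "Changes in HOMA-IR would be calculated between the responder and relapser groups". No test, model, covariate, stratification or matching is given for this contrast.
- **Population (same paragraph).** "we will confine the analysis to nondiabetic subjects (about 80%) of those with W60 samples". "This would comprise about 250 subjects with available W60 sera", split evenly at 125 per group.
- **Follow-on stage (Materials and Methods, Longitudinal study, Aim 6 paragraph).** "A group of matched (BMI, race, HCV genotype) non-diabetic controls with no virologic response at TW20 will also be studied", but only "if a difference in IR is detected at TW 60 between patients with SVR and relapsers". TW20 insulin assays in study subjects and controls depend on the same condition.
- **Link with response (Background and Significance).** Higher BMI is cited as associated with poorer response to interferon and ribavirin.

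The multivariable models elsewhere in Data Analyses concern steatosis, fibrosis or virologic response. None has HOMA-IR or its change as the dependent variable.

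**The concern.** Whether a patient keeps or loses the virologic response is not randomized. If SVR patients and relapsers differ at baseline in a factor that also affects HOMA-IR at week 60, or its course up to then, part of the observed difference belongs to that factor and not to clearance. The plan controls BMI, race and genotype by matching at the second stage and leaves them uncontrolled at the first.

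The order matters because the first comparison decides whether the second takes place. A confounded contrast can start the TW20 work without cause, or hide a real difference so that the work never starts. Matching the later controls does not repair the SVR-versus-relapser estimate, since those controls do not enter it.

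**Working it through.** **The plan's figures.** 250 / 2 = 125 per group, which agrees with the stated split. 250 / 0.80 = 312.5, so about 312 patients with week 60 sera are implied; the documents do not state that total. No alpha, power, SD or effect size is given for Aim 6, so there is no power figure to reproduce.

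**Assumed inputs (not in the documents).** Two-sided alpha 0.05; SD of log HOMA-IR 0.7 at each time; correlation of baseline with week 60 of 0.6; no true effect of clearance unless stated.

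- SD of log change = 0.7 × √(2 × (1 − 0.6)) = 0.626.
- SE of the group difference = 0.626 × √(2/125) = 0.079.
- Detectable difference at 80% power = 0.354 SD, or 0.354 × 0.626 = 0.222 log units.

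**Bias from an uncontrolled factor.** Bias = (imbalance in prevalence) × (difference in log trend between patients with and without the factor). The trend difference is assumed to be 0.20 log units, which is 0.20 / 0.626 = 0.32 SD of change. Rejection probability = Φ(b/SE − 1.96) + Φ(−b/SE − 1.96).

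| Scenario | Bias b (log) | b/SE | False positives |
|---|---|---|---|
| No imbalance | 0 | 0 | 5% |
| One factor, 10-point imbalance | 0.10 × 0.20 = 0.02 | 0.25 | 5.7% |
| One factor, 20-point imbalance | 0.20 × 0.20 = 0.04 | 0.5 | 8.0% |
| Three such 20-point factors, one opposed | 0.04 + 0.04 − 0.04 = 0.04 | 0.5 | 8.0% |
| Three such 20-point factors, all aligned | 3 × 0.04 = 0.12 | 1.5 | 33% |

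**Bias toward the null.** With a true difference of 0.222 and an opposing bias of 0.04, (0.222 − 0.04) / 0.079 = 2.30. Power is then Φ(2.30 − 1.96), about 63% instead of 80%.

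**Second check, in SD units.** Take a continuous confounder with group imbalance d (in SD) and correlation r with HOMA-IR change, so that bias = d × r and SE = √(2/125) = 0.126. For d = 0.3 and r from 0.1 to 0.4, the false-positive rate is 5.6% to 15.8%. For d = 0.5 and the same r, it is 6.8% to 35.3%. In a simulation of 4,000 runs for each of five scenarios, putting the confounder in the model gave 4.7% to 5.7%.

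**Level versus change.** These figures are for change. In a comparison of week 60 levels, a stable effect of BMI, race or genotype on HOMA-IR passes directly into the contrast, because nothing is subtracted. The follow-on condition in Materials and Methods is worded as a difference in insulin resistance at TW60, so the trigger may be read as a comparison of levels. The documents give no figure from which to size that case.

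**The case against.** The strongest reply is that the plan already has protection and that the documents show no imbalance. Much of this stands. Change from baseline removes any stable effect of the three factors on the level of HOMA-IR, so they must act on the change itself to do harm, and no section says they do. Excluding diabetics removes one confounder, and week 60 timing is meant to limit drug effects and on-treatment weight loss. None of these steps balances baseline BMI, race or genotype, and the first does not apply if week 60 levels are compared.

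It can also be said that Aim 6 is the last of six aims, that the consequence of the trigger is further assays, and that missing covariates are part of a generally brief analysis section. That limits the stakes. But where the plan wants multivariable analysis it says so, and a two-group comparison carried out as written would be unadjusted.

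Four stronger readings are tempting and are not supported:

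- **That the plan expects SVR patients and relapsers to differ on these factors, because the cross-sectional analyses (item 4) test them as predictors of SVR.** Item 4 counts every W20 non-responder as no SVR, whereas Aim 6 compares SVR with relapse among W20 responders. Testing a candidate predictor is also not expecting a difference.
- **That the matching admits confounding of this contrast.** The plan gives no reason for the matching, and it serves a different comparison. The cited BMI finding concerns response to treatment, not relapse after a TW20 response. For race and genotype, the only support is their choice as matching factors.
- **That the matched controls are a fallback for a failed first comparison.** They are studied only after a difference has been found.
- **That a false-positive rate of one third is to be expected.** It needs three 20-point imbalances, each with a 0.20 log trend difference, all in one direction.

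**Conclusion.** The point holds as an avoidable gap in the Aim 6 analysis. Groups formed by outcome are compared with partial protection and without adjustment for three baseline factors that the plan itself controls at the next stage. That unadjusted result decides whether the next stage happens.

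The actual bias is unknown and could be nil. Under the stated assumptions, a single factor with a 10- to 20-point imbalance raises the false-positive rate from 5% to about 6% to 8%, and the 33% case is pessimistic. All these rates rest on an SD, correlation, imbalance and trend difference from outside the documents. The case for change does not depend on their exact size, because the remedy is cheap and the imbalance cannot be ruled out in advance. It is a recommended change, not a flaw that invalidates the study.

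**What to change.** Pre-specify one model for Aim 6: a linear regression of log HOMA-IR at week 60 on response group (SVR versus relapse), with baseline log HOMA-IR, baseline BMI, race and HCV genotype as covariates. With baseline log HOMA-IR in the model, using log change as the outcome gives the same group coefficient, so this also settles the level-or-change ambiguity. State the coding of race and genotype before the data are seen.

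Name the adjusted estimate as the Aim 6 result and as the criterion for going on to the TW20 assays and matched controls. Report the unadjusted difference beside it, with a table of the three factors by group so that the imbalance can be seen.

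The cost is plan wording and a few degrees of freedom out of about 250 patients. No new data are needed: BMI and genotype are already in the baseline data list, as is ethnicity, which is assumed here to supply the race variable used for matching.

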Appendix A: Directions for determining waist circumference

1. Record waist circumference at screening (S00), month 24 (M24) and month 48 (M48) visits. This will be recorded on Form #11, Physical Exam.

Waist Circumference Measurement Instructions

- To define the level at which waist circumference is measured, a bony landmark is first located and marked.
- The patient stands, and the examiner, positioned at the right of the patient, palpates the upper hipbone to locate the right iliac crest. (See figure below.)
- Just above the uppermost lateral border of the right iliac crest, a horizontal mark is drawn, and then crossed with a vertical mark on the midaxillary line.
- The measuring tape is placed in a horizontal plane around the abdomen at the level of this marked point on the right side of the trunk.
- The plane of the tape is parallel to the floor, and the tape is snug, but does not compress the skin.
- The measurement is made at normal minimal respiration.
- Record the circumference in units (cm or in) that were used on the measuring instrument. It is not necessary to record both centimeters and inches.
- Round centimeters to the nearest cm. Round inches to the nearest inch.
